The aim of this study is to perform a randomised controlled trial to study the changes in motor evoked potential amplitudes comparing sugammadex and placebo.

2. Background

Intraoperative monitoring (IONM) is most frequently employed in patients where the spinal cord or nerves are considered at risk. This may be evident through patient symptoms, pathological process or appearance on imaging.

Trained neurophysiologists that work in concert with the surgeon and anaesthesiologist perform the intraoperative monitoring. The monitoring commences once the patient has received general anaesthesia. Small electrodes are placed under the skin of the scalp and peripheries and different electrical stimuli are delivered to evoke a measured response. The neurophysiologist is able to monitor different potentials (motor evoked potentials, somatosensory evoked potentials, electromyography) and assess for a significant change.

Motor evoked potential monitoring is a well-established and safe intervention to assist in prevention of intraoperative injury during spine surgery.(Schwartz, Sestokas et al. 2011) There is no current consensus for criteria for change in amplitude for trans-cranial motor evoked potential monitoring. The peak-peak amplitude of the baseline motor evoked potential is utilised as a monitoring tool during surgery. The smaller the change in amplitude that is utilised as alarm criterion the more false positives that will be conveyed to the surgeons. (Legatt, Emerson 2016) Our neurophysiologists use a decrease in the amplitude by more than 50% or loss of the signal as a trigger to warn the surgeon of potential development of a neurological insult or injury.

The usual anaesthetic practice at our institution for patients undergoing posterior cervical spine surgery is to administer muscle relaxation to aid intubation at the start of the case and occasionally small doses of rocuronium (10-20mg) prior to turning the patient prone. The neuromuscular blockade is then allowed to wear off and the neurophysiologist will attempt to record their baseline motor evoked potentials during or just prior to surgical exposure.

A peripheral nerve monitor may be used to monitor the degree of residual neuromuscular blockade. This is standard anaesthetic equipment with the most common mode to assess residual blockade used being a train of four count. This involves adhesive dots applied over the ulna nerve and a current applied (approximately 70-80mA) in a train of four impulses 0.5 seconds apart with a pulse width of 250 microseconds. It is a safe method of assessing the occupancy of

acetylcholine receptors at the neuromuscular junction by observing the number of twitches displayed in the peripheral muscle (e.g thumb movement).

Number of twitches

- 0- 100% receptors blocked
- 1- 90% receptors blocked
- 2- 75-80% receptors blocked
- 3- 75% receptors blocked
- 4- 0% receptors blocked

For the purposes of our study we plan to continuously monitor the train of four count and ratio using a peripheral nerve stimulator module that is built into the anesthesia machine (GE Datex Ohmeda). The train of four count on both measuring tools will be delivered as a train of four impulses 0.5 seconds apart (2Hz) at 70-80mA with a pulse width of 250 microseconds.

Our current approach does not involve routine measurement of the degree of residual neuromuscular blockade with a peripheral nerve stimulator. This is a safe approach as monitoring is achievable with partial blockade but may not necessarily be most beneficial in patients with existing neurological impairment as complete reversal of neuromuscular blockade is not ensured.(Li, Song et al. 2010)

The issues with this current technique are;

- a) Patients cannot be monitored for neurological changes during their transfer into the prone position
- b) There is likely residual neuromuscular blockade decreasing the amplitude of motor evoked potentials

A cases series of 10 patients in healthy subjects undergoing lumbar spine surgery demonstrated a 74% increase in mean amplitude of the MEPs with reversal of neuromuscular blockade with sugammadex 2mg/kg.(Batistaki, Papadopoulos et al. 2012)

We plan to perform a randomised controlled cross over trial comparing the change in MEP amplitudes with administration of sugammadex or placebo. This will be performed on at risk patients (e.g. cervical myelopathy) undergoing posterior cervical spine surgery where MEPs can be more difficult to attain but of higher utility.(Kombos, Kopetsch et al. 2003)

The crossover arm of the trial is to enable patients to function as their own control group. During surgical closure patient will remain on a total intravenous anaesthesia (propofol and remifentanil). When the patient returns to a train of four count of 2 or more on peripheral nerve monitor repeat motor evoked potentials will then be recorded and

patients will receive the alternate drug to the one received in the initial arm of the trial.

The purpose of this study is to determine the increase in amplitude of the motor evoked potentials when residual neuromuscular blockade is reversed with sugammadex or placebo.

4. Hypothesis

We hypothesize that reversal of neuromuscular blockade by sugammadex will increase the amplitude of motor evoked potentials compared with placebo.

5. Significance of the study

Facilitating increased amplitudes of MEPS via reversal of residual neuromuscular blockade will enable increased accuracy of monitoring.

Providing the option of reversal of neuromuscular blockade will allow MEPs to be monitored during patient positioning to prevent placing them in a neurologically compromising position.

6. Methods

6.1 Research Design

This is a prospective, single centre, triple blinded randomised controlled cross-over trial. Patients who are scheduled for an elective posterior cervical spine procedure in prone position and require motor evoked potential monitoring (MEPs) will be included. Patients will be randomised to assign to one of the following treatment sequences: sugammadex followed by placebo, or vice versa. The primary outcome is the change of MEP amplitude of the first dorsal interossei from baseline 3 minutes after administration of the allocated intervention. The patients, anesthesiologists and neurophysiologists (outcome assessor) will be blinded for the allocated intervention group.

The first study intervention will be performed after the patients are positioned in prone with a train of four count of 2 and satisfactory baseline motor evoked potentials have been recorded. This will likely occur during or just prior to surgical exposure.

The second study intervention will be performed during surgical closure. This will be once the surgeons have completed their use of motor evoked potentials and the patient remains on total intravenous anaesthesia (propofol and remifentanil). A minimum washout period of 100 min after the last bolus dose of rocuronium (equivalent to 5 half lives) is required and the completeness of washout will be confirmed with no residual tetanus fade, fade on train of four (or fading in double burst stimulation) on a peripheral nerve stimulator. The operative time

of posterior cervical spine procedure is usually around 3 hours and should allow complete washout of rocuronium. After the preconditions are achieved on peripheral nerve stimulator or the direct train of four monitor, the second intervention (either sugammadex or placebo) will be administered.

On each occasion the increase in amplitude of the motor evoked potential of both upper and lower limbs will be assessed at 3,6,9,12 and 15 minutes post intervention.

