6.4 Randomisation Method

Enrolled patients will be randomised according to a computer based, permuted block randomisation method, with a 1:1 allocation ratio and a variable block size of 4-6.

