8.2 Outcome Measurements

Primary Outcome Measure

The primary outcome measure is the increase in amplitude of the motor evoked potential measurements of the first dorsal interosseous muscle at 3 minutes following reversal of residual muscle relaxation with either sugammadex or placebo.

Secondary Outcome Measures

- Changes in the amplitude of the MEPs from the baseline in the first dorsal interosseous muscle at 6 and 9 minutes

- Side effects of reversal (hemodynamic changes, respiratory changes, surgeon observed patient movement, requirement for additional muscle relaxation and the anesthetic agents)
- Grading of relaxation of the surgical field by the surgeons using a four-point Likert scale (poor, acceptable, good and optimal) .

9. Data Collection and Management

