10.2 Sample size

A previous observational study reported sugammadex increased the amplitude of MEP by 74% (Batistaki, Papadopoulos et al. 2012). The normal upper limb MEP amplitude (first dorsal interosseus) is 2000 +/- 1600 microV from a previous published cross-over study in MEP (Chong, Manninen et al. 2014). Based on the assumption that the within-patient standard deviation of the MEP amplitude is 1600 microV and a power of 80%, a total of 30 patients is required in this two-intervention crossover study for detecting a treatment difference of 1200 microV (60% increment) at a two-sided 0.05 significance level. The sample size will be increased to 40 patients (20 patients per group) to cater for a potential 15-25% drop-out rate during the study.

11. Analysis

Statistical analysis will be performed using SPSS statistical software (version 14). The data distributions will be tested for normality with the Kolmogorov-Smirnov test. Descriptive statistics will be summarised as mean (\pm SD), median [Interquartile range (IQR)] or number (%) as indicated. The Mann-Whitney U test will be performed to compare the amplitude values of the two groups. TOF count, grades of surgical relaxation will be compared using the Chi-square test or Fisher's exact test according to the expected counts. In all cases, a P-value of 0.05 will be considered statistically significant.

12. Ethical aspects

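### The pre-dose MEP enters the primary outcome only by subtraction; prespecifying it as a period-specific covariate would protect power against an unstated pre/post correlation

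*Combined protocol and SAP*

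**What the plan says.** Section 6.1 states: "The primary outcome is the change of MEP amplitude of the first dorsal interossei from baseline 3 minutes after administration of the allocated intervention". Section 8.2 agrees in substance: "The primary outcome measure is the increase in amplitude of the motor evoked potential measurements of the first dorsal interosseous muscle at 3 minutes" after the study drug.

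A pre-dose reading is planned before each dose. Section 7.2 has baseline MEPs taken before the first study drug. For the second period, the crossover paragraph ahead of section 4 says that "repeat motor evoked potentials will then be recorded" before the alternate drug is given. The section 7.2 text on the second period does not repeat this.

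Section 10.2 sizes the trial on the SD of the amplitude, not of the change: "Based on the assumption that the within-patient standard deviation of the MEP amplitude is 1600 microV and a power of 80"%. The target is "detecting a treatment difference of 1200 microV (60% increment) at a two-sided 0.05 significance level", and "a total of 30 patients is required in this two-intervention crossover study". No correlation between pre-dose and post-dose readings is given.

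For amplitude, section 11 names a Mann-Whitney U test between the two groups. It has no covariate, no patient term and no period term, and does not say whether the tested value is the change or the 3-minute reading.

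**The concern.** Subtraction gives the pre-dose reading a fixed weight of 1. The weight that minimises error variance is the slope of the 3-minute reading on the pre-dose reading within patient. With equal SDs that slope is r. If r is low, subtraction adds the noise of the baseline to the noise of the outcome. With equal SDs and r below 0.5, the change is noisier than the 3-minute reading alone.

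Replacing the unpaired test with a paired one does not remove this, because a correctly paired test of changes still fixes the weight at 1. At stake is whether the primary comparison reaches the 80% power that section 10.2 claims.

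The plan gives some reason not to take a high r for granted. Section 7.2 allows testing at a train-of-four count of 2 or more, and section 2 associates counts from 2 to 4 with very different receptor blockade. Part of the pre-dose variation may therefore be depth of block, which sugammadex is meant to remove before the 3-minute reading. This is inference; under placebo r may well be higher.

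**Working it through.** **Inputs.** From section 10.2: SD = 1600 microV, difference = 1200 microV, two-sided alpha 0.05, N = 30 evaluable and 40 enrolled. From section 6.4: 1:1 allocation to the two sequences. Assumed: r from 0 to 0.75; equal pre-dose and post-dose SDs unless stated; errors independent between periods; normal-theory tests.

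**Step 1: reproduce the plan.** In a balanced two-period crossover the treatment effect has SE = SD × √(2/N).
- SE = 1600 × √(2/30) = 413.1.
- Noncentrality = 1200/413.1 = 2.905.
- On 28 df, power is 80.1%, so the stated 30 reproduces.
- The inflation reproduces too: 30/(1 − 0.25) = 40.

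**Step 2: error SD per period under each analysis.**
- Change score: 1600 × √(2(1 − r)), N − 2 = 28 df.
- Covariate: 1600 × √(1 − r²), N − 3 = 27 df, with the variance multiplied by 1 + 1/(N − 4) = 1 + 1/26 because the slope is estimated.
- Before that penalty, the variance ratio of covariate to change score is (1 − r²)/(2(1 − r)) = (1 + r)/2.

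**Step 3: power at N = 30.**

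| r | Change SD | Change power | Covariate SD (with penalty) | Covariate power |
|---|---|---|---|---|
| 0 | 2262.7 | 50.9% | 1630.5 | 78.5% |
| 0.25 | 1959.6 | 62.9% | 1578.7 | 81.0% |
| 0.5 | 1600.0 | 80.1% | 1412.0 | 88.7% |
| 0.7 | 1239.4 | 95.1% | 1164.4 | 97.0% |
| 0.75 | 1131.4 | 97.7% | 1078.5 | 98.6% |

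A simulation of the 2×2 crossover (4000 runs per setting) agrees: change score 50.6%, 81.3% and 95.2% at r = 0, 0.5 and 0.7; covariate 78.2%, 89.4% and 97.0%.

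**Step 4: more completers.** At 15% dropout, 40 × 0.85 = 34 complete. Change score versus covariate is then 56.4% v 83.8% at r = 0 and 85.0% v 92.5% at r = 0.5. If all 40 complete: 63.7% v 89.6% and 90.5% v 96.1%.

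**Step 5: unequal SDs.** Let the pre-dose SD be 0.6 of the post-dose SD. The change SD is 1600 × √(1 + 0.36 − 1.2r), the covariate SD is as before, and the best slope is r/0.6. At N = 30:

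| r | Best slope | Change power | Covariate power |
|---|---|---|---|
| 0 | 0 | 67.2% | 78.5% |
| 0.3 | 0.50 | 80.1% | 82.1% |
| 0.5 | 0.83 | 89.5% | 88.7% |
| 0.7 | 1.17 | 97.3% | 97.0% |

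With the best slope near 1, subtraction is already close to optimal and the covariate costs up to about 1 point.

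**Step 6: if 1600 is the SD of the change.** The change score then has 80.1% at every r. The covariate, at equal SDs, gives 88.7% at r = 0.5, 84.6% at 0.7 and 80.5% at 0.9.

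**The case against.** The strongest reply is that the change score is valid and matches the trial's stated purpose, so this is a matter of efficiency and not an error. That stands. So do these points:

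- **The comparator is hypothetical.** Section 11 does not specify a paired change-score test. The powers above describe what a paired analysis of the stated outcome would achieve, not the Mann-Whitney test as written. A within-patient analysis has to replace that test before any covariate can be added.
- **r = 0 is extreme.** It says that, once the patient effect is removed, readings minutes apart under one anaesthetic are no more alike than readings from opposite ends of an operation of about 3 hours. Some positive correlation is likely.
- **The SD does not inform r.** A reader might infer a low r from an SD that is 80% of the mean (1600/2000). The size of an SD says nothing about a correlation. If 1600 includes between-patient spread, the true within-patient SD is smaller and both powers are higher.
- **The covariate does not always win.** A reader might infer from (1 + r)/2 that the change score can never be better. That ratio needs equal SDs and a known slope. A smaller pre-dose SD is plausible here, because those readings are taken under partial block and section 10.2 expects a marked rise. Step 5 shows that the gain can then vanish.
- **The period 2 baseline is post-randomisation.** It follows the first drug, so carry-over could affect it. The change score has the same exposure.

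None of this shows material harm from adjustment.

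**Conclusion.** The point holds as one of precision and is worth acting on. Sections 6.1 and 8.2 use the pre-dose MEP only by subtraction, section 11 uses no covariate, and the planned power is tied to the SD of an amplitude with nothing to link it to the SD of a change. On the assumptions listed, adjustment is worth about 28 points of power at r = 0, 18 at r = 0.25, 9 at r = 0.5 and 1 at r = 0.75. If the pre-dose SD is about 0.6 of the post-dose SD and r is 0.5 or more, it gives no gain and costs about 1 point.

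A reader might infer that the trial has only 51% power. The documents do not support that: the figure needs r = 0, exactly 30 completers, equal SDs and a literal reading of 1600 microV as the SD of one amplitude. The case for the covariate is that r is unknown, and adjustment keeps power at about 78% or more across the settings examined, while the change score may or may not.

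**What to change.** - **Section 11, primary analysis.** As part of a within-patient crossover analysis replacing the unpaired test, regress the within-patient difference (period 1 minus period 2) in 3-minute amplitude on sequence and on the corresponding difference in pre-dose amplitude. With sequence coded +1 and −1, its coefficient is the treatment effect. This is equivalent to a model with patient, period, treatment and the pre-dose MEP of that period. The covariate must be period-specific, because a single baseline per patient cancels.
- **Other time points.** Use the same model at 6 and 9 minutes, and report raw change descriptively.
- **Section 7.2.** State that a pre-dose MEP is recorded before the second study drug, as the crossover paragraph ahead of section 4 already says.
- **Carry-over.** Note that this second pre-dose reading follows the first drug, and plan to examine carry-over into it.

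Cost: one degree of freedom, and about 1 to 2 points of power against ignoring the baseline if r is 0 (80.1% to 78.5%). No measurement is needed beyond those already planned. The text change is larger than adding a covariate term, since section 11 has no within-patient model yet.

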7.2 Study Protocol

Patients should undergo peripheral nerve monitoring following the induction via a peripheral nerve stimulator and by a direct train of four monitor by the neurophysiologists. The train of four should be assessed on peripheral nerve stimulator and on the neurophysiology monitoring prior to turning the patient prone. If the patient has two or more twitches on either monitoring they should be given 0.1mg/kg rocuronium prior to positioning prone.

Once the patient is in their final position for surgery the anaesthetic will be changed to a total intravenous anaesthetic (TIVA) with propofol and remifentanil titrated to entropy of 40-60. The volatile anaesthesia has to be washed out with high flows of 10L/min until end tidal desflurane is less than or equal to 0.2.

When the above conditions are met the train of four count (TOFC) will be checked by the anaesthesiologist. When the TOFC is 2 or more the baseline motor evoked potentials (bMEPs) will be performed.

Following the bMEPs the anaesthesiologist will administer the reversal drug (either sugammadex 2mg/kg in 10 ml syringe or matching placebo). This time must be strictly recorded, as it is the time that has elapsed since the induction dose of muscle relaxant. The neurophysiologist will perform and record MEPS at 3,6 and 9 minutes post reversal dose. The following parameters will continuously be monitored during the study period: TOFC, Entropy, BP, HR, CO2,

peak airway pressures, anaesthetic infusion rates, temperature and oxygen saturation. If the testing occurs during surgical exposure it is important to ask the surgeons to make a very brief pause to allow the motor testing to be performed and to check the entropy at the same time.

Following surgery commencement there will be a surgical grading of the relaxation of the surgical field once exposure attained and collection of surgeon stated observation of patient movement.

The operative time of posterior cervical spine procedure is usually around 3 hours and should allow for complete washout of rocuronium. A minimum washout period of 100 min after the last bolus dose of rocuronium (equivalent to 5 half-lives) is required and the completeness of washout will be confirmed with no residual tetanus fade, no fade on train of four (or fading in double burst stimulation) on a peripheral nerve stimulator.

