The crossover arm of the trial will occur during surgical closure at the end of the operation when the surgeons have finalised their use of the monitoring and the patients are still receiving total intravenous anaesthesia (propofol and remifentanil). If needed, each patient will be given 0.1mg /kg rocuronium to facilitate surgical closure. When the train of four count is of 2 or more the patients will be administered the cross-over drug (placebo if received sugammadex initially and vice versa) and the motor evoked potentials and same anaesthetic variables as above will be recorded for 3,6 and 9 minutes post cross-over dose.

8. Assessment

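### Section 6.1 sets a wider MEP schedule (both limb levels, out to 15 minutes) than Sections 7.2 and 8.2, so the extra recordings may be omitted or, if made, have no stated outcome status

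*Combined protocol and SAP*

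**What the plan says.** Three sections of the combined protocol and SAP describe the post-dose MEP assessments.

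- **Section 6.1 (Research Design)**, for each of the two periods: "the motor evoked potential of both upper and lower limbs will be assessed at 3,6,9,12 and 15 minutes post intervention".
- **Section 7.2 (Study Protocol)**, first period: "The neurophysiologist will perform and record MEPS at 3,6 and 9 minutes post reversal dose". For the second period, MEPs and the anaesthetic variables "will be recorded for 3,6 and 9 minutes post cross-over dose". Neither sentence names a muscle or limb.
- **Section 8.2 (Outcome Measurements)** has one secondary MEP item: "Changes in the amplitude of the MEPs from the baseline in the first dorsal interosseous muscle at 6 and 9 minutes". No outcome is listed for the lower limbs or for 12 or 15 minutes.

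The primary outcome is consistent. Section 6.1 has "The primary outcome is the change of MEP amplitude of the first dorsal interossei from baseline 3 minutes after administration of the allocated intervention", and Section 8.2 likewise takes "measurements of the first dorsal interosseous muscle at 3 minutes following reversal of residual muscle relaxation with either sugammadex or placebo".

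Section 9.1 defines the outcome data to be collected by reference to Section 8. Section 11 names a Mann-Whitney U test for amplitude without giving a muscle, limb or time, and then states: "In all cases, a P-value of 0.05 will be considered statistically significant". It contains no multiplicity rule.

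**The concern.** The protocol gives two answers to which recordings are to be made. Under 7.2 the neurophysiologist can stop at 9 minutes, and the 12- and 15-minute assessments promised in 6.1 are then missing. Under 6.1 those data and the lower-limb data are collected, but neither the outcome list nor the analysis section says what they are for. An effect that persists to 15 minutes, or one seen in the legs, could then be reported as a finding at 0.05 or left out, with nothing in the plan to show which was intended.

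This affects only the secondary evidence. There is also a small practical side: Section 7.2 asks the surgeons to pause briefly when testing falls during exposure, so the number of recordings is not free.

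**Working it through.** **1. The plan's own figure.** The only related calculation is the sample size in Section 10.2, checked here to confirm that it does not depend on the disputed schedule.

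- Inputs (Section 10.2): within-patient SD 1600 microV, difference 1200 microV, two-sided 0.05, power 80%.
- Normal approximation, with variance of the paired difference 2 × SD²: N = 2 × (1.960 + 0.842)² × (1600/1200)² = 2 × 7.849 × 1.778 = 27.9, so 28.
- Noncentral t with N − 2 degrees of freedom: power is 78.6% at N = 29 and 80.1% at N = 30. The stated 30 is reproduced.
- Drop-out: 30/0.85 = 35.3, so 36; 30/0.75 = 40. The stated 40 covers the upper end of the 15–25% range.

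None of these inputs involves the lower limbs or any time after 3 minutes.

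**2. The sections side by side.**

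| Section | Times (min) | Site |
|---|---|---|
| 6.1, both periods | 3, 6, 9, 12, 15 | upper and lower limbs |
| 7.2, period 1 | 3, 6, 9 | not named |
| 7.2, period 2 | 3, 6, 9 | not named |
| 8.2, primary | 3 | first dorsal interosseous |
| 8.2, secondary | 6, 9 | first dorsal interosseous |

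On recording times, 6.1 and 7.2 differ by 12 and 15 minutes. On site, 6.1 and 8.2 differ by the lower limbs and by any upper-limb muscle other than the first dorsal interosseous. Section 7.2 is silent on site.

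**3. Recordings.** Two periods × 3 times = 6 per patient, against 2 × 5 = 10. Over 40 patients with no losses: 240 against 400. Over 30 completers: 180 against 300.

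**4. Secondary MEP comparisons.**

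- Section 8.2: 6 and 9 minutes, so 2.
- Section 6.1: 2 limb levels × 5 times = 10, less the primary, so 9. This assumes one measure per limb level; the documents do not give the number of muscles.

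**5. Chance of at least one false positive at 0.05 each, with no true effect.**

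- Independent tests: 1 − 0.95² = 0.0975; 1 − 0.95⁹ = 0.370.
- Correlated tests: simulation of 400,000 draws per setting, two-sided 1.96 cut-off, assumed correlations 0.5 to 0.9 between times and 0.3 to 0.8 between limbs. The result is 7.0% to 9.1% for 2 tests and 14.8% to 30.4% for 9.

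The documents give no correlations, so the last line is a range under assumption.

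**The case against.** The strongest reply is that the documents already indicate which list governs. Section 9.1 sends the reader to Section 8 for outcome data, Section 8.2 has an explicit secondary list, and Section 6.1 never calls its wider assessments outcomes. A 15-minute or lower-limb result would therefore be post hoc by default. This largely stands. A reader might infer that the whole secondary outcome set is open to choice after the data are seen; the documents do not support that. What remains unsettled is whether the extra recordings are to be made and how they are described if they are.

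Three further limits also stand.

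- A reader might infer that the sections cannot all be followed. They can: recording both limb levels at all five times satisfies every recording in 7.2 and every MEP outcome in 8.2. Section 7.2 does not say that recording must stop at 9 minutes.
- A reader might infer that 7.2 confines recording to one hand muscle. It names none. The muscle comes from 8.2, which lists outcomes and is not a recording schedule.
- Section 9.1 mentions an attached data collection form that is not in the text available. It may fix the times and muscles.

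It can also be said that Section 11 names no test of lower-limb or late readings, so the 9 comparisons are a possibility and not a plan. That is right, and the error rates should be read as showing what the plan leaves room for. The objection does not remove the mismatch itself: 7.2 repeats its three times for the second period, so a single slip there is unlikely, and nothing explains the two additional times in 6.1.

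**Conclusion.** The inconsistency is real and minor. It concerns two time points per period and the lower-limb readings, and it bears on secondary evidence only. It gives no ground for inferring that the 3-minute primary comparison or its power is compromised.

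If 6.1 is followed and every reading is tested, the secondary MEP comparisons rise from 2 to 9, and the chance of at least one false positive from about 10% to 37% under independence. Independence is implausible for repeated readings in the same patient; about 7–9% against 15–30% is more realistic under the assumed correlations. These figures rest on one measure per limb level and on all readings being tested at 0.05. They leave out the non-MEP secondary outcomes. A count of 10 against 3 would overstate the point, because it includes the primary on both sides.

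**What to change.** Before the data are examined, put one list of times and muscles into Sections 6.1, 7.2 and 8.2, and check the data collection form against it. There are two ways to do this:

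1. Delete 12 and 15 minutes and the lower limbs from 6.1. This costs wording only.
2. Keep them: add the times and named muscles to 7.2, and list them in 8.2 as exploratory outcomes to be reported in full whatever the result. This costs two more recordings per period, with extra surgical pauses where testing falls during exposure.

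In Section 11, state which muscle and times are analysed. Analyse the listed first dorsal interosseous times in one within-patient repeated-measures crossover model, with treatment, period, sequence and time, plus treatment-by-time so that each time has its own contrast. The 3-minute contrast is primary; 6 and 9 minutes are secondary. This replaces separate Mann-Whitney comparisons at 0.05, which treat the two treatments as independent groups and do not use the within-patient pairing on which the sample size relies. The cost is a short rewrite of Section 11, including the scale of analysis: with an amplitude of 2000 ± 1600 microV in Section 10.2, skewness is likely and any transformation should be stated in advance.
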